6.2 Exclusion Criteria

Exclusion Criteria: Each participant who meets any of the criteria below will be excluded from study participation:

1. Participant and/or study partner anticipates being unable to attend all visits and complete all study activities during the trial.
2. Women of child-bearing potential who are pregnant or plan to become pregnant during the course of the trial. ****Women of child-bearing potential, who are not abstinent or exclusively in same sex relationships must test negative for pregnancy as indicated by a negative urine pregnancy test and agree to use an approved contraception method listed in section 6.4 for the entirety of the study.*
3. Has any significant co-morbidity/condition, planned surgery or participation in another clinical trial which may either prevent safe participation in the study

procedures or interfere with the evaluation of safety or efficacy of the study Device as a potential treatment for PDD.

4. In the Investigator's opinion, has severe dementia, (e.g., MMSE (at screen visit) <15 and/or requires significant assistance with ADLs due to cognitive deficits).
5. Has experienced a myocardial infarction, angina, or stroke within the past 12 months, transient ischemic attack (TIA) within the past 6 months or has a documented aspiration event in the medical records.
6. Are receiving late-stage therapies for PD (e.g., deep brain stimulation or pump infusion therapies) or are being treated with another neurostimulation device.
7. History of interventional brain surgery or have received magnetic resonance guided high intensity focused ultrasound.
8. Demonstrate suicidality at screening (scores ≥ 4 on the Columbia- Suicide Severity Rating Scale (C-SSRS) Baseline "In the past Month" section).
****Participants that respond affirmatively to questions 4 or 5 on the C-SSRS should receive a referral for mental health counseling according to local site regulations and standards.*
9. Have been previously diagnosed with either clinically meaningful central vestibular dysfunction (lifetime) or have experienced clinically meaningful peripheral vestibular dysfunction within the last 12 months.
10. Use any drugs excluded in the Excluded Medications List.
11. Use of antipsychotic medication(s) listed in the Approved Concomitant Medications (i.e., pimavanserin and quetiapine) that have not been taken for more than 180 days and does not have medical record documentation of normal QTc interval (i.e., no prolongation of the QTc interval) as measured via electrocardiogram after starting the medication.
12. Have active ear infections, perforated tympanic membrane or labyrinthitis, as identified by a general ear examination performed by medically qualified Investigators or have chronic tinnitus that has been ongoing for at least 3 months.
13. Have a cochlear implant, myringotomy tubes or hearing aids that cannot be easily/reliably removed for treatment.
14. Clinically significant abnormalities in B12, thyroid function, blood count, comprehensive metabolic panel or urinalysis results tested at the study screen. Screening tests are not required in cases where test results within normal range within 6 months of study screen are documented in the medical records.

6.3 Concomitant Therapy

6.3.1 Approved Concomitant Medications

- The use of the FDA-approved pharmaceutical medications to treat the cognitive symptoms including cholinesterase inhibitors, glutamate N-methyl-D-aspartate (NMDA) receptor regulators and combination therapies will be permitted during the study so long

as the type or dose does not change during the study or the 4 weeks immediately preceding the study screening visit.

- The use of the following medications used to treat motor and non-motor symptoms associated with PD will be permitted during the study so long as the type or dose does not change during the course of the study or the 4 weeks immediately preceding the study screening visit: oral levodopa-based therapies, transdermal DRTs (e.g., rotigotine transdermal system), dopamine receptor agonists, MAO-B inhibitors and COMT inhibitors.
- The use of selective serotonin reuptake inhibitors or other anti-depression/anti-anxiety medications not specifically excluded in the Excluded Medications list will also be permitted during the study so long as the type or dose does not change during the study or the 12 weeks immediately preceding the study screening visit.
- The use of orexin receptor antagonists for the treatment of insomnia will be permitted during the study so long as the type or dose does not change during the study or the 4 weeks immediately preceding the study screening visit.
- The use of pimavanserin and quetiapine QHS at doses that do not produce cognitive deficits or daytime sleepiness will be permitted during the study so long as the medication has been taken for > 180 days and the type or dose does not change during the study or the 4 weeks immediately preceding the study screening visit.
- Medications prescribed for other concomitant illnesses are allowed so long as they are not listed in the Excluded Medications list.
- Vaccines, supplements, and over the counter medications, including those taken occasionally (for example: seasonal allergy medications), should be documented if a dose occurred during the protocol timeframe.
- When medications are prescribed for indications other than symptoms associated with PD or cognition, physicians will be encouraged to utilize the one that is least likely to impact symptoms assessed in the trial. In particular, the central anticholinergic properties of medications should be considered.
- Changes to medications for symptoms associated with cognition are not permitted during the trial. Participants will be advised that during the trial, they should maintain patterns of usage of approved therapeutic medications that they normally use and that they should not initiate new medication (type, dosage or route of administration), medicating patterns or other interventions unless their provider deems the change to be medically necessary, as changes in concomitant treatments will interfere with the ability to attribute clinical change during the study to use of the Device. Any medically necessary changes will be recorded as concomitant medications and participants will continue in the study. Reasons for changes in medications used to treat cognitive symptoms will be recorded and participants who make changes to these medications or add new medications likely to modulate symptoms associated with cognition during the study will be included in the ITT analysis but excluded from the PP analysis.

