5.3 Justification for Treatment Protocol

The results from the single-site RCT provide evidence to support the safety and effectiveness of TNM™ Device treatments for managing the symptoms associated with PD, experienced by those that have PDD. TNM™ Device treatments in this study utilized the same time-varying waveform and BID schedule as was used in a pivotal study that demonstrated TNM™ is a safe and effective prophylactic for episodic migraine. The study described herein will utilize the same active treatment waveform and BID treatment regimen as were used in these previous studies.

In this study, participants will treat for 12 weeks (84 days) rather than 8 weeks (56 days), as was the case for the single-site RCT. The selection of a longer treatment interval was based on the finding that the treatment response, including measures of relevance to PDD, did not reach an asymptote during the 8 weeks of treatment. These results suggest that additional gains may be obtained with longer treatment intervals. Notably, 12-week treatment intervals were shown to be safe for the indication of episodic migraine, and there has been no evidence from a small crossover study in PD that treatment intervals of 12-16 weeks of treatments increases the risk of device-related AEs relative to 8 weeks. The treatment interval in this study will be limited to 12 weeks to minimize confounding variables that may arise with participants changing concomitant medications.

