6.1. ANALYSIS POPULATIONS

Intent-to-treat Population (ITT): All participants who start at least one treatment with the study device will be included in this primary analysis of efficacy and safety.

Per-protocol Population (PP): All eligible participants who (1) demonstrate at least 70% adherence of the randomized expected treatments with the Study Device and (2) have completed the regularly scheduled end of treatment visit (day 84), and (3) have not had changes to medications used to treat motor and/or non-motor symptoms of PD during the trial will be included in the PP population.

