6.4.3. Pre-study and Concomitant Medications

The number and percentage of each treatment cohort on concomitant therapies at randomization will be reported categorically including the following:

- o adenosine A2A antagonists
- o amantadine
- o anticonvulsants
- o anti-depressant/antianxiety medications
- \circ antiemetics
- \circ antihistamines
- o antihypertensives
- o antipsychotics
- central anticholinergics
- cognitive enhancers
- COMT Inhibitors
- contraceptives
- o corticosteroids
- o dystonia treatments
- o incontinence treatments
- inhaled levodopa
- o inhaled or ingested cannabinoids
- laxatives/stool softeners
- MAO-B inhibitors
- o narcotics
- o oral or transdermal dopamine agonists
- o oral levodopa-based therapies
- o oral levodopa-based therapies/COMT inhibitors
- o orthostatic hypotension treatments
- o pain/cramping treatments
- pump therapies
- o sexual dysfunction treatments
- o sialorrhea treatments
- o sleep aids
- o stimulants

Changes in medications to treat symptoms associated with PD during the trial are a protocol deviation. Changes in these medications would exclude participants from the PP analysis. Changes in medications in the ITT cohorts will be summarized descriptively.

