6.6.1 PRIMARY ENDPOINTS

(Safety) MDS-UPDRS Parts I, II & III summed score: Changes will be considered to be clinically meaningful worsening if the median difference meets or exceeds the previously established MCID (+5.2 points for clinical worsening) (Makkos, Kovacs et al. 2018). Two-sided, 90% confidence intervals for the combined MDS-UPDRS Parts I, II, and III scores at baseline and the end of treatment period will be constructed. If the median difference (baseline- end of treatment) is less than 5.2 and the confidence interval of the difference (baseline – end of treatment) contains 5.2, then the no clinically meaningful worsening.

(Feasibility)

- **Retention rate** will be defined by the percentage of participants that complete assessments required for analysis of the secondary endpoint:
 - High retention: >90%
 - Moderate retention: 60-90 %
 - Low retention: < 60 %
- **Treatment adherence** rate for each participant will be defined as the percentage of twice-daily treatments with the neuromodulation device completed during the 12-week treatment period:
 - High adherence: >84%
 - Moderate adherence: 55-84 %
 - Low adherence: < 55 %
 - Treatment adherence is captured by the study device and will be reported summarized with minimum, 1Q, median, 3Q, and maximum values. Treatment adherence of \geq 70% is required for inclusion in the Per Protocol cohort.

Adverse Events (AEs): Participants will be assessed for AEs every two weeks at minimum (either at study visits or during phone calls). For each group, the AEs will be summarized with frequency and percentage by preferred (PT) term, with all participants in that treatment group as the denominator. Classification will utilize MedDRA System Organ

Class (SOC) based on MedDRA® Version 26.0 or other terminology/classification common to Parkinson's disease (e.g., falls, freezing of gait, etc.). AE incidence will be summarized by both severity and causal relationship to Device treatment (as determined by the blinded Principal Investigator or designated study personnel). AEs deemed to be of "possible" or "probable" relationship or "related" to the Device will also be considered as device related. Additionally, the number of events and number of device-related events per person will be reported as a distribution.

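### The primary safety verdict makes no allowance for PD medication increased because of worsening, so both ITT and PP can lean toward a finding of no clinically meaningful worsening

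*Protocol*

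**What the plan says.** **Endpoint and verdict.** SAP 2.2 defines the safety endpoint as the change in summed MDS-UPDRS Parts I, II and III from Day 0 to Day 84. SAP 6.6.1 sets the rule: "Changes will be considered to be clinically meaningful worsening if the median difference meets or exceeds the previously established MCID", with the MCID put at +5.2.

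**Medication changes during treatment.** Protocol 6.3.1 discourages them but allows those a provider judges medically necessary: "Any medically necessary changes will be recorded as concomitant medications and participants will continue in the study". The same section explains the discouragement: "changes in concomitant treatments will interfere with the ability to attribute clinical change during the study to use of the Device". Protocol 5.3 says treatment was "limited to 12 weeks to minimize confounding variables that may arise with participants changing concomitant medications".

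**ITT.** SAP 6.1: "All participants who start at least one treatment with the study device will be included in this primary analysis of efficacy and safety". Nothing is conditional on medication.

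**PP.** Under SAP 6.1, PP participants must, among other conditions, "have not had changes to medications used to treat motor and/or non-motor symptoms of PD during the trial". SAP 6.4.3 adds: "Changes in these medications would exclude participants from the PP analysis. Changes in medications in the ITT cohorts will be summarized descriptively". Protocol 6.3.1 is narrower. Only those who change medication for cognitive symptoms, or add medication likely to affect cognition, are "included in the ITT analysis but excluded from the PP analysis", and only for the cognitive medications does it expressly ask for the reason to be recorded.

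**Silence.** Neither document says how a PD medication increase is handled in the safety analysis. MDS-UPDRS is also collected at Day 42, but no analysis rule uses it.

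**The concern.** The safety question is whether PD signs and symptoms worsen on tvCVS. A participant who worsens may be given more PD medication. If that works, the Day 84 score looks better than the course that prompted it, and ITT takes the score at face value. Under the SAP's definition, PP drops the participant altogether. The two populations lose the information by different routes, so their agreement is weak evidence that medication changes did not matter. There is no control arm against which a masked drift could show, and a median of 12 values can move several points when one or two participants change sides.

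What is at stake is the wording of the primary safety conclusion: a statement of no clinically meaningful worsening that rests partly on additional PD treatment, without the reader being told so.

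**Working it through.** The plan states no figure for the effect of medication changes, so there is none to reproduce. What follows applies the SAP rule to assumed data. Worsening is end of treatment minus baseline, so positive is worse (SAP 6.6.1 writes the difference the other way round, a separate matter). The threshold is 5.2 and n = 12.

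**1. Example (assumed changes)**

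All worsening counted: −4, −2, 0, 1, 2, 6, 7, 8, 9, 10, 12, 14. Median = (6 + 7)/2 = 6.5, which meets the worsening rule.

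Suppose the two worst (12 and 14) have PD medication increased.

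| Handling | Middle values | Median | 90% signed-rank CI |
|---|---|---|---|
| All worsening counted | 6, 7 | 6.5 | 2.0 to 8.5 |
| ITT, near-complete reversal (12→0, 14→1) | 1, 2 | 1.5 | 0.5 to 5.5 |
| ITT, half reversal (12→6, 14→7) | 6, 6 | 6.0 | 1.5 to 7.0 |
| PP under the SAP, n = 10 | 2, 6 | 4.0 | 0.5 to 7.5 |

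The near-complete-reversal ITT result and the PP result both have a median below 5.2 and an interval containing 5.2, which SAP 6.6.1 reads as no clinically meaningful worsening. Half reversal leaves the ITT verdict unchanged. PP is 4.0 however much is reversed.

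Tipping point in ITT: if a fraction r of both worsenings is reversed, the values become 12(1−r) and 14(1−r). Once both lie between 2 and 6 they are the two middle values, with mean 13(1−r). This equals 5.2 at r = 0.60, so the ITT verdict flips only above 60% reversal in this data set.

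Under the protocol's narrower PP definition, a motor-medication increase would not remove these two. If they met the other PP conditions they would stay in with their post-change scores, as in ITT.

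**2. Simulation (40,000 trials per setting)**

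The documents give no SD. Back-solving the two sample-size illustrations with a normal approximation:

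- SAP section 4 (mean 6.2, MCID 5.20, 80%): SD = (6.2 − 5.2)/0.842 × √12 ≈ 4.1.
- Protocol 10.1 (mean 12.9, MCID 6.70, 90%): SD = (12.9 − 6.7)/1.282 × √12 ≈ 16.8.

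Assumed: normal changes, true mean worsening 8 points, and half of those worsening by 10 or more given an increase (about 2.5 of 12 at SD 10). The entries are the probability that the median is at least 5.2.

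| SD | All counted | ITT, full reversal | ITT, half reversal | PP (SAP) |
|---|---|---|---|---|
| 4.1 | 0.98 | 0.75 | 0.96 | 0.92–0.93 |
| 10 | 0.79 | 0.22 | 0.75 | 0.51 |
| 16.8 | 0.69 | 0.12 | 0.65 | 0.35 |

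The ITT loss is large only when reversal is close to complete. The PP loss does not depend on reversal.

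**3. Worst-rank check**

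Placing the two participants at the top of the ordering leaves the 6th and 7th values at 6 and 7, so the median returns to 6.5 whatever was reversed. For n = 12 the interval from the 3rd to the 10th ordered value has coverage 1 − 2(1 + 12 + 66)/4096 = 0.961; the 4th to 9th gives 1 − 2(1 + 12 + 66 + 220)/4096 = 0.854, short of 90%. The usable interval in the example is therefore 0 to 10. With three or more worst-ranked participants its upper limit can only be stated as at least the MCID.

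**The case against.** **ITT is not blind to these participants.** It keeps everyone treated and uses the Day 84 score, so residual worsening counts. A reader might infer that neither population registers the worsening; that is true of ITT only if reversal is complete. This objection stands and limits the size of the effect.

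**The bias need not run one way.** The SAP's PP exclusion applies to any PD medication change, including reductions and changes unrelated to worsening. An increase may also reflect progression or fluctuation rather than the device. This stands as a caution. The direction is clear only for increases prompted by worsening.

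**Such cases are captured elsewhere.** Worsening may be reported as an adverse event, and AEs and medications are reviewed at every scheduled contact after baseline. SAP 6.4.3 makes a PD medication change a protocol deviation; deviations are source-verified and summarised, and an independent medical monitor reviews safety. This makes full concealment unlikely, but none of it enters the median rule.

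**Consequence and frequency.** A reader might infer that the decision to proceed to a Phase II trial hangs on this verdict. The stated criteria in Protocol 10.1 and SAP section 4 are no SADEs and at least 75% completion; the MDS-UPDRS median is not among them. Entry also requires an expectation of stable medication, and two increases with near-complete reversal is an assumed scenario.

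**Observed scores are a legitimate choice.** Using the Day 84 value regardless of medication is a recognised treatment-policy approach. Making a worst-rank composite primary would count every such increase as device-era failure with no comparator. This stands, so the composite belongs in a sensitivity analysis.

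**Conclusion.** The gap is real and should be fixed before analysis. The plan expects medication changes, says that they confound attribution to the device, keeps the participants on study, and gives the primary safety verdict no rule for them. The observed ITT score hides worsening to the extent that medication reverses it, and the SAP's PP definition removes it entirely. The SAP and protocol also define the PP exclusion differently and must be reconciled.

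The size depends on how many participants have medication increased for worsening and how far it helps, and the documents give neither. In the assumed example the ITT verdict flips only above 60% reversal in two of 12, while PP falls below 5.2 at any degree of reversal. The calculations use the SAP's 5.2; Protocol 10.1 uses 6.70, against which the example's 6.5 would not have been flagged at all.

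The documents do not support saying that worsening is lost from both populations in every case, that the bias always runs toward safety, or that the Go/No-Go decision is compromised.

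**What to change.** - **SAP 6.6.1.** Keep the observed Day 84 ITT analysis as primary. Add a pre-specified sensitivity analysis in which any participant whose PD medication was increased or added for worsening is ranked as worsened by at least the MCID (worst rank), with an order-statistic confidence interval for the median.
- **Reporting.** Give the number of such participants beside the verdict. If the two analyses disagree, do not state the absence of clinically meaningful worsening without qualification.
- **Protocol 6.3.1.** Extend the recording of reasons from cognitive medications to all PD motor and non-motor medication changes, so that these participants can be identified.
- **PP definition.** Reconcile Protocol 6.3.1 with SAP 6.1 and 6.4.3 on which medication changes exclude a participant.

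The cost is a few lines of SAP text, one form field, a little more analysis and a somewhat more conservative safety statement. Patient care does not change.

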6.3.2 Excluded concomitant medications, drugs and supplements

- Off-state rescue medications (e.g., apomorphine injections or levodopa-based inhalers) are not permitted on days of study center visits but may be used at other times. Protocol deviations will not be accepted, and the visit should be rescheduled in circumstances

where off-state rescues were taken on the day of a visit. Off-state rescue medications may otherwise be used throughout the trial period.

- Antipsychotic Medications not specifically listed in the Approved Concomitant Medications (i.e., either neuroleptics or atypical antipsychotics).
- Medications producing side effects of cognitive deficits, delirium, psychosis, motor impairments or daytime sleepiness. For example, benzodiazepines such as clonazepam may produce cognitive deficits, however, these may be avoided at low dosages (i.e., \leq 1mg) and/or with QHS administration and therefore would be permitted under these conditions.
- Mucuna pruriens supplements
- Anti-emetics (e.g., 5-HT₃ receptor antagonists, D₂ receptor antagonists, first-generation H₁ Receptor antagonists, muscarinic antagonists, synthetic cannabinoids or SP/NK₁ receptors antagonists with anti-emetic properties) as well as corticosteroids with significant anti-emetic properties prescribed chronically (taken more than 2 times per week, consistently)
- Inhaled or ingested cannabinoids (e.g., marijuana, tetrahydrocannabinol, nabilone or cannabidiol) within 4 weeks of screening and during the study period.
- Any drug that has not been legalized on a United States Federal level
- Controlled substances that have not been prescribed under the care of a licensed professional.
- Anticholinergics with definite central activity (acbcalc.com)
- Antibody therapies used to treat cognitive decline in Alzheimer's disease (e.g., those that target amyloid).

